**Additional Study Investigators:**

[name]  
[name], M.Sc.  
[name] [name]  
[name]  
[name]  
[name] Sc.M.  
[name]  
[name]  
[name], MS

**1. Abstract** (Provide no more than a one page research abstract briefly stating the problem, the research hypothesis, and the importance of the research)

Within the last decade, Linac based stereotactic body radiation therapy (SBRT) has been shown to be an effective treatment option for pancreas and liver tumors. SBRT delivers high doses of radiation therapy to the tumor over only 1-5 treatments. Because of the spatial precision of SBRT, it is feasible to administer a high radiation dose in only a few treatments. By minimizing the amount of radiation to surrounding healthy tissue, it is possible to decrease the rate of toxicity/complication and increase the radiation dose to cancerous tissue, thereby allowing better local control.

SBRT of the abdomen has been limited by the movement of intra-abdominal organs that naturally occurs with respiration and bowel movement. Organ motion occurs both intra- and interfractionally.

While intrafractional motion is a result of respiration, peristalsis and cardiac motion, the magnitude of interfractional target motion is dependent of daily variations in organ filling, weight change, tumor growth and radiation induced changes of tissue. Tumor movement may lead to tumor displacement and suboptimal dose delivery. Accurate localization of the target is very important to improve treatment delivery accuracy and reduce toxicity of the treatment. To evaluate tumor motion due to breathing motion, a 4-D CT simulation scan is performed. If the tumor moves more than 3 mm during a breathing cycle, breathing motion management is employed using Active Breathing Control (ABC) technique. ABC requires the patient to hold his/her breath within the proper tidal volume while treatment is delivered, while free breathing may be resumed between periods of treatment. This technique limits the delivery of RT to specific phases of the respiratory cycle so as to minimize the influence of breathing on the delineated tumor.

Despite significant progress made in ABC technique, tumor and organ motion could only be minimized and not eliminated completely. Assessing patient specific tumor/organ motion (both intra- and interfractional) throughout the course of SBRT treatment offers the possibility of ensuring delivery of the prescribed target dose while simultaneously minimizing normal tissue damage. In order to monitor the abdominal soft tissue motion, the Department of Radiation Oncology has developed a 4D ultrasound technique based on an ultrasound probe holder and a continuous motion monitoring software.

The 4D ultrasound image is acquired by using a motorized 3D ultrasound probe and image continuously. 4D ultrasound is a new non-ionizing and non-invasive imaging technique that allows continuous image acquisitions for real-time motion monitoring during the radiation treatment. Ultrasound is a proven modality for soft tissue localization (ref-prostate-breast). Several studies  have shown that even with older version of ultrasound system, the ultrasound images correlates with CT images within a small absolute magnitude of difference (about 3 mm), therefore we expect to have good agreement between the reference CT simulation and reference 4D ultrasound. Ultrasound motion monitoring during treatment delivery is based on real-time automatic registration of ultrasound images acquired on treatment days to reference ultrasound images acquired at the beginning of treatment, thus removing any inter-modality tracking uncertainty and inter-user variability. The ultrasound probe in the CT image will be contoured and radiation beams that directly pass through the ultrasound probe will be avoided. An SBRT treatment plan usually consist of multiple (9 – 12 beams for IMRT technique) co-planar beams delivered around the isocenter placed inside the tumor. Omitting the small range of angle directly passing through the ultrasound probe will not compromise the treatment plan dosimetry quality.

The first arm of this study is designed to validate the accuracy and stability of the ultrasound system and establish an efficient workflow to be applied for cancer patients. Healthy volunteers are able to perform more regular breathing patterns and longer breath-holds. Scanning healthy volunteers allows more predictable data acquisition time point and opportunity to develop a general workflow that can be continuously optimized for patient scanning. Anatomical abnormalities (surgical implant, fibrosis and metastases) in patients might produce artifacts in ultrasound images that can reduce motion tracking accuracy. Ultrasound of healthy volunteer with better anatomical landmark visualization helps us to evaluate the stability and accuracy of the ultrasound system and registration software.

For patient study, organ motion registered by ultrasound will be compared to motion recorded by CBCT and the accuracy of the ultrasound system will be evaluated. In addition, imaging and setup efficiency, cost and volume acquisition rate will be compared between CBCT based and 4D ultrasound based intra-fraction motion monitoring.

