## **3. Background**

SBRT of the abdomen has been limited by the movement of intra-abdominal organs that naturally occurs with respiration and bowel movement. Currently at Johns Hopkins Hospital, breathing motion management is employed using ABC technique for patient treated with pancreas and liver SBRT if the tumor and/or abdominal organs move more than 3 mm during a breathing cycle. While ABC device has been reported to reduce respiratory motion to below 2 mm, small variation of breath-holds may lead to tumor displacement and suboptimal dose delivery. Assessing patient specific tumor/organ motion (both intra- and interfractional) throughout the course of SBRT treatment offers the possibility of ensuring accurate delivery of the prescribed target dose while simultaneously minimizing normal tissue damage. This can be achieved by using Clarity 3D ultrasound system together with ABC device for real-time tracking of the pancreas and liver during SBRT treatment.

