## **4. Study Procedures**

- a. **Arm 1:** Validate the ultrasound tracking and establish reference range of motion for abdominal soft tissue motion from healthy individuals.

Fifteen healthy volunteers will be enrolled and informed consent obtained per study guidelines as described. A reference ultrasound scan will be conducted on each subject during breath-hold. Subjects will be required to lie in supine position and engaged with ABC; an ultrasound probe will be placed at the abdomen area with minimal pressure applied. Continuous motion monitoring is achieved by acquiring 4D ultrasound images using a motorized 3D ultrasound probe to image the pancreas, liver and other intra-abdominal organs continuously. Several 4D ultrasound scans will be collected during subsequent breath-holds that serve as secondary images. Registration of the reference and secondary ultrasound scans will be performed with automated registration algorithm built-in with the ultrasound system to evaluate abdominal soft-tissues and organs motion. Additional registration of ultrasound images will be performed with Velocity software to evaluate accuracy of automated registration software in the ultrasound system.

- b. **Arm 2:** Monitor the abdominal soft tissue motion of pancreas patients treated with SBRT during the whole course of treatment.

Thirty pancreatic cancer patients receiving SBRT treatment with ABC will be enrolled and informed consent obtained per study guidelines as described. A 4D ultrasound scan will be acquired at the time at simulation and used as a reference ultrasound image for localizing

tracking target. The ultrasound probe will be placed at the abdominal area to monitor the pancreas motion. The probe will remain in place during the CT scan. Patient setup and the ultrasound probe location will be recorded so that the same setup can be reproduced during treatment delivery. The ultrasound probe in the CT image will be contoured and radiation beams that directly pass through the ultrasound probe will be avoided.

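### Does the undefined zero for the ultrasound and CBCT values, with two dates given for the reference ultrasound, undermine the accuracy analysis?

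*Combined protocol and SAP*

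**What the plan says.** Section 7a says the ultrasound software produces a curve of motion over time. Accuracy is the difference between that curve and CBCT at the CBCT times, reported with descriptive statistics and a 95% confidence interval. It names no origin, and it does not say whether either series is reset at each fraction.

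Other sections supply most of what is missing:

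- Section 1 (Abstract), on what is compared: "organ motion registered by ultrasound will be compared to motion recorded by CBCT". Section 4 repeats this for Arms 2 and 3.
- Section 4, on the ultrasound reference in Arm 2: "A 4D ultrasound scan will be acquired at the time at simulation and used as a reference ultrasound image for localizing" the tracking target, with the same instruction for Arm 3. On the setup: "The probe will remain in place during the CT scan".
- Section 4, on the CBCT reference: intra-fraction CBCT is registered to the reference CT.
- Section 1, on the date of the reference ultrasound: tracking rests on "real-time automatic registration of ultrasound images acquired on treatment days to reference ultrasound images acquired at the beginning of treatment". This differs from section 4.
- Section 1, on ultrasound against CT: earlier studies found agreement to about 3 mm, and on that basis "we expect to have good agreement between the reference CT simulation and reference 4D ultrasound".
- Section 3, on residual motion: "While ABC device has been reported to reduce respiratory motion to below 2 mm, small variation of breath-holds may lead to tumor displacement".

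**The concern.** Primary objective c rests, in the patient arms, on one subtraction. If the two series have different or unknown zeros, the result mixes tracking error with whatever separates those zeros, and a reader of the mean and interval cannot tell which is described.

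Two readings seem possible. Both values could be positions in one common frame, or each could be displacement from its own modality's reference. On the same images the two differ by exactly the distance between the reference ultrasound and the reference CT. The only size the documents offer for ultrasound-to-CT disagreement is about 3 mm, which is 3/2 = 1.5 times the 2 mm ceiling quoted for respiratory motion under ABC.

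The conflicting dates appear to make this worse. With ultrasound zeroed on the first treatment day and CBCT on the simulation CT, any organ shift between those days would enter the difference one for one. The Arm 1 check does not help: "Additional registration of ultrasound images will be performed with Velocity software to evaluate accuracy of automated registration software in the ultrasound system" compares ultrasound with ultrasound.

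**Working it through.** The plan states no numerical figure on this point, so there is none to reproduce. The check is algebra on one axis for one patient.

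**Notation.** Let x_t be the true organ position at a CBCT time, x_U its position at the reference ultrasound, and x_C its position at the reference CT. Let b be a constant ultrasound-minus-CT offset for that patient, and e_t the tracking error. Then:

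- US_t = x_t + b + e_t and US_ref = x_U + b
- CBCT_t = x_t and CT_ref = x_C

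**Reading A, common frame.** A = US_t − CBCT_t = b + e_t.

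**Reading B, displacement from own reference.** B = (US_t − US_ref) − (CBCT_t − CT_ref) = e_t − (x_U − x_C).

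**Gap.** A − B = b + (x_U − x_C), the full distance between the two references. The readings do differ, but they carry different errors. The inter-modality offset b appears only in A. A real difference in organ position between the reference scans appears only in B.

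**Where the 3 mm belongs.** The Abstract's figure describes ultrasound against CT, so it is a value for b. Take b = 3 mm, organ displacement 1.5 mm, x_U = x_C = 0 and no tracking error:

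- Reading A: (0 + 1.5 + 3) − 1.5 = 3 mm.
- Reading B: [(0 + 1.5 + 3) − (0 + 3)] − 1.5 = 0 mm.

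The result under B is 0 for every patient, even if b varies from patient to patient.

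**Size under A.** If the 3 mm offset points the same way in everyone, the mean moves by 3 mm. If its direction is random in three dimensions (assumption), the per-axis SD is 3/√3 = 1.73 mm. The 95th percentile of the absolute shift in an arm mean is then about 1.96 × 1.73/√30 = 0.62 mm in Arm 2 and 1.96 × 1.73/√20 = 0.76 mm in Arm 3. A simulation of 20,000 runs gave the same values.

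**Size under B.** The term left is x_U − x_C. With one reference pair per patient and between-patient SD τ for that term, the 95% interval half-width for an arm mean cannot fall below t × τ/√n. The documents give no τ, and the 3 mm does not supply one. The values below are illustrative assumptions.

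| τ (assumed) | Arm 2, n = 30, t = 2.045 | Arm 3, n = 20, t = 2.093 |
|---|---|---|
| 0 mm | 0 mm | 0 mm |
| 1.0 mm | 0.37 mm | 0.47 mm |
| 1.5 mm | 0.56 mm | 0.70 mm |

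**Which reading the plan supports.** Ultrasound is registered to ultrasound, CBCT is registered to CT, the ultrasound output is a motion curve, and the stated comparison is of motion with motion. All four fit B. Reading A needs the two modalities in one coordinate frame, and the documents do not say that such a frame is set up.

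**Reset at each fraction.** If both series were zeroed at the start of a fraction, the difference would be (US_t − US_0) − (CBCT_t − CBCT_0) = e_t − e_0. Both b and x_U − x_C then drop out.

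**The date.** A first-day ultrasound zero with a simulation CT zero would shift the difference by the displacement D between those days. The documents give no D; an assumed range of 0 to 5 mm gives a shift of 0 to 5 mm. Section 4 does not lead there, since it sets both references at simulation. The Abstract itself pairs the reference ultrasound with the simulation CT and has the probe contoured on the CT image, so its phrase is out of step with its own surroundings.

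**The case for a change.** The strongest case for a change is that section 7a holds the whole patient-arm accuracy analysis and leaves its central quantity partly undefined. Objective c speaks of intra-fraction monitoring, while section 7a also wants interfractional variation; a fraction-start zero and a simulation zero serve these aims differently. Reading B still relies on two separately acquired reference scans. Section 3 allows that breath-holds vary, and no check of the two references against each other is planned. Pilot data with an unclear origin are harder to reuse.

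Parts of this stand. Section 7a does lack the sentence, nothing says whether values are reset per fraction, and the Abstract's date is wrong against section 4. The size does not stand. The 3 mm cancels on the reading the plan supports. The 2 mm is a reported ceiling on respiratory motion, not a figure for breath-hold variation, and it is not all the motion followed, because interfractional motion is studied too. The 1.5 ratio therefore compares unlike bounds.

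An added report of the distance between the two references would need a common frame that the documents do not establish. It would also mix inter-modality error with breath-hold difference, so it could not identify the cause.

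**Conclusion.** The concern does not call for a change. The missing origin is a detail that section 4 lets an analyst fill sensibly: each modality's displacement from its own simulation reference. The Abstract's date is a clerical slip beside two consistent instructions in the operative section.

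On that reading a constant inter-modality offset adds 0 mm. The figure of up to about 3 mm arises only if ultrasound is placed in CT coordinates with the offset left in, the reading with less support. What remains is any real shift of the organ between the two simulation scans. The documents do not quantify it, and keeping the probe in place during the CT helps tie the two scans to the same setup.

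This rests on section 4 being followed, on the offset being constant within a patient, and on both series being treated alike if they are reset per fraction. The stakes are limited: section 7a sets no acceptance margin for accuracy, section 7c describes the data as pilot, and section 4 keeps the ultrasound out of clinical decisions.

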## **2. Objectives** (include all primary and secondary objectives)

### Primary objectives:

- a. Establish effective workflow for real time monitoring of abdominal soft-tissue motion due to respiration using 4D ultrasound system
- b. Evaluate feasibility of real time motion monitoring of tumor and surrounding organ/tissue during pancreas and liver SBRT treatments using 4D ultrasound system
- c. Evaluate accuracy of the 4D ultrasound motion monitoring system compare to CBCT based intra-fraction motion monitoring during pancreas and liver SBRT treatments

### Secondary objective:

- a. Evaluation of dosimetry differences due to target/organ motion observed

## **3. Background**

SBRT of the abdomen has been limited by the movement of intra-abdominal organs that naturally occurs with respiration and bowel movement. Currently at Johns Hopkins Hospital, breathing motion management is employed using ABC technique for patient treated with pancreas and liver SBRT if the tumor and/or abdominal organs move more than 3 mm during a breathing cycle. While ABC device has been reported to reduce respiratory motion to below 2 mm, small variation of breath-holds may lead to tumor displacement and suboptimal dose delivery. Assessing patient specific tumor/organ motion (both intra- and interfractional) throughout the course of SBRT treatment offers the possibility of ensuring accurate delivery of the prescribed target dose while simultaneously minimizing normal tissue damage. This can be achieved by using Clarity 3D ultrasound system together with ABC device for real-time tracking of the pancreas and liver during SBRT treatment.

## **4. Study Procedures**

- a. **Arm 1:** Validate the ultrasound tracking and establish reference range of motion for abdominal soft tissue motion from healthy individuals.

Fifteen healthy volunteers will be enrolled and informed consent obtained per study guidelines as described. A reference ultrasound scan will be conducted on each subject during breath-hold. Subjects will be required to lie in supine position and engaged with ABC; an ultrasound probe will be placed at the abdomen area with minimal pressure applied. Continuous motion monitoring is achieved by acquiring 4D ultrasound images using a motorized 3D ultrasound probe to image the pancreas, liver and other intra-abdominal organs continuously. Several 4D ultrasound scans will be collected during subsequent breath-holds that serve as secondary images. Registration of the reference and secondary ultrasound scans will be performed with automated registration algorithm built-in with the ultrasound system to evaluate abdominal soft-tissues and organs motion. Additional registration of ultrasound images will be performed with Velocity software to evaluate accuracy of automated registration software in the ultrasound system.

- b. **Arm 2:** Monitor the abdominal soft tissue motion of pancreas patients treated with SBRT during the whole course of treatment.

Thirty pancreatic cancer patients receiving SBRT treatment with ABC will be enrolled and informed consent obtained per study guidelines as described. A 4D ultrasound scan will be acquired at the time at simulation and used as a reference ultrasound image for localizing

tracking target. The ultrasound probe will be placed at the abdominal area to monitor the pancreas motion. The probe will remain in place during the CT scan. Patient setup and the ultrasound probe location will be recorded so that the same setup can be reproduced during treatment delivery. The ultrasound probe in the CT image will be contoured and radiation beams that directly pass through the ultrasound probe will be avoided.

On each treatment day, 4D ultrasound images will be acquired continuously during beam on time to monitor pancreas motion. The system will record all relevant images, but will not be used in clinical decision making. These data will be used to evaluate the magnitude of target motion and dosimetry deviation due to the motion. Intra-fraction CBCT images acquired during treatment will be registered with reference CT images. Organ motion registered by ultrasound will be compared to motion recorded by CBCT and the accuracy of the ultrasound system will be evaluated.

c. **Arm 3:** Monitor the abdominal soft tissue motion of liver patients receiving SBRT treatment with ABC during the whole course of treatment.

Twenty hepatic cancer patients being treated with SBRT treatment will be enrolled and informed consent obtained per study guidelines as described. A 4D ultrasound scan will be acquired at the time at simulation and used as a reference ultrasound image for localizing tracking target. The ultrasound probe will be placed at the abdominal area to monitor the liver motion. The probe will remain in place during the CT scan. Patient setup and the ultrasound probe location will be recorded so that the same setup could be reproduced during treatment delivery. The ultrasound probe in the CT image will be contoured and radiation beams that directly pass through the ultrasound probe will be avoided.

On each treatment day, 4D ultrasound images will be acquired continuously during beam on time to monitor liver motion. The system will record all relevant images, but will not be used in clinical decision making. These data will be used to evaluate the magnitude of target motion and dosimetry deviation due to the motion. Intra-fraction CBCT images acquired during treatment will be registered with reference CT images. Organ motion registered by ultrasound will be compared to motion recorded by CBCT and the accuracy of the ultrasound system will be evaluated.

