## 7. Study Statistics

a. Analytic plan for primary objectives:

An effective workflow for real time monitoring of abdominal soft-tissue due to respiration using a 4D ultrasound system will be developed through the use of healthy controls. As

described earlier, these controls will provide data for estimating the background reference for abdominal soft tissue. Data collected on controls will be summarized with descriptive statistics. Quantitative analysis of target/organ motion and displacement recorded in 4D real-time ultrasound scan will be carried out to assess both intra- and interfractional variation as described above in the study. This study will help us to ensure delivery of the prescribed target dose while simultaneously minimizing normal tissue damage. We will consider the approach feasible if we are able to successfully complete the procedure and output the associated data for 50% of the study participants. The software will output a motion curve over time. We will calculate the difference between values on the curve and the values from CBCT at the specific time points that CBCT is performed, and summarize the differences using descriptive statistics. A 95% confidence interval for the difference will be reported. These data will be used to evaluate the accuracy of the 4D ultrasound system.

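### Arm 1 is presented as an accuracy validation, but its only comparison measures agreement between two registration programs

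*Combined protocol and SAP*

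**What the plan says.** Two places set the aim of Arm 1. The Abstract (section 1) states that "The first arm of this study is designed to validate the accuracy and stability of the ultrasound system", and adds that "Ultrasound of healthy volunteer with better anatomical landmark visualization helps us to evaluate the stability and accuracy of the ultrasound system and registration software". The second sentence names the system and the software as separate things to be evaluated. Section 4a opens with the aim "Validate the ultrasound tracking and establish reference range of motion for abdominal soft tissue motion from healthy individuals".

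The procedure in section 4a has two registration steps. First, "Registration of the reference and secondary ultrasound scans will be performed with automated registration algorithm built-in with the ultrasound system". Then, "Additional registration of ultrasound images will be performed with Velocity software to evaluate accuracy of automated registration software in the ultrasound system". Several scans are taken per volunteer over successive breath-holds.

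For analysis, section 7a says of this arm that "Data collected on controls will be summarized with descriptive statistics". It names no measure of agreement between the built-in and Velocity results.

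The independent comparator belongs to the patient arms. The Abstract sets this out in the sentence that begins "For patient study, organ motion registered by ultrasound will be compared to motion recorded by CBCT and the accuracy of the ultrasound system will be"; sections 4b and 4c repeat this, and primary objective c in section 2 defines accuracy against CBCT.

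**The concern.** A claim about the accuracy of a measuring system needs a reference that does not share the system's errors. For volunteers the plan describes no CT, CBCT, phantom, imposed displacement or landmark-based reference. Good landmark visibility is given as a reason for using volunteers, but no procedure uses landmarks as a standard. What remains is one set of ultrasound images registered by two programs.

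Close agreement would show that the programs give similar answers, not that the answers are right. Poor agreement would show that at least one program is in error, but not which one.

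At stake is what Arm 1 may conclude. With the aim worded as it is, a small between-program difference could be read as evidence of system accuracy and placed beside the CBCT comparison, which does use an independent modality. The analysis is also underspecified: several scans from one volunteer are not independent, and nothing says that the Velocity registration is done without knowledge of the built-in result.

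**Working it through.** The plan states no precision, power or error figure for Arm 1, and section 7c says the variability is unknown. There is no figure to reproduce. The check concerns what the comparison can measure.

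**Inputs from the documents.** Arm 1 has 15 volunteers with several scans each; the index method is the built-in registration; the comparator is Velocity on ultrasound images (section 4a); the analysis is descriptive (section 7a).

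**Model.** For one displacement between a reference and a secondary scan, let T be the true motion, S the error carried by the images that acts equally on both programs, and e1 and e2 the program-specific errors.

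- Built-in reading = T + S + e1
- Velocity reading = T + S + e2
- Difference = e1 − e2
- True error of the built-in reading = S + e1

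T and S cancel in the difference, whatever their size. With independent errors and a common program SD σ, the SD of the difference is √2 × σ, and the SD of the true error is √(SD(S)² + σ²).

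**Illustration.** Assume σ = 0.5 mm. The SD of the difference is √2 × 0.5 = 0.71 mm in every row.

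| Assumed SD of S (mm) | SD of true error (mm) | True error SD ÷ difference SD |
|---|---|---|
| 0 | √(0 + 0.25) = 0.50 | 0.7 |
| 0.25 | √(0.0625 + 0.25) = 0.56 | 0.8 |
| 0.5 | √(0.25 + 0.25) = 0.71 | 1.0 |
| 1.0 | √(1 + 0.25) = 1.12 | 1.6 |
| 1.5 | √(2.25 + 0.25) = 1.58 | 2.2 |

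The two SDs are equal where SD(S) = σ. Below that point the between-program SD overstates the true error; above it, it understates it.

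**Simulation.** A separate run used n = 15, one difference per volunteer, σ = 1 mm and 20,000 replicates. Shared bias was set at 0, 1, 2 and 3 mm and shared SD at 0, 1 and 2 mm. In all twelve combinations the mean difference was about 0.00 mm, its SD was about 1.41 mm (√2 × 1), and the 95% interval covered zero about 95% of the time. The root mean square of the true error rose from 1.0 mm with no shared error to 3.7 mm at the extreme (√(3² + 2² + 1²) = 3.74). The between-program result did not respond to shared error at all.

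**The case against.** The strongest case on the other side has five parts.

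- **The section 4a sentence on Velocity claims only software accuracy.** That is so. The system-level claim is in the Abstract, and the criticism rests on reading the two together. Even for software alone, a second program is a comparator and not a standard.
- **No formal objective needs Arm 1 for accuracy.** This stands. Section 7a uses the controls for workflow and a background reference, and its difference and 95% confidence interval are for ultrasound against CBCT. A reader might infer that the study has no independent accuracy reference; the documents do not support that.
- **Arm 1 does more than re-register images.** Also true. It serves workflow development, repeated breath-hold scans and a reference range of motion, and those aims are sound.
- **Cancellation is not total.** Arm 1 measures displacement between scans, so a constant image offset is not an error in the motion estimate. Artefacts cancel only if both programs respond to them alike. The documents do not say whether Velocity is run automatically or with operator guidance. Nor do they state that both programs read identical images, though that is the natural reading of section 4a. The point is therefore limited to errors that affect both programs alike.
- **The harm is conjectural.** A reader might infer that Arm 1 must make the system look better than it is, or that its result will be reported as validated accuracy. Neither follows: the direction depends on unknown error sizes, and no section commits to such a report. Ultrasound is also not used for clinical decisions.

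These parts narrow the point. None of them supplies the reference that the Abstract's claim needs.

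**Conclusion.** The point holds as a mismatch between the accuracy claim for Arm 1 and what its comparison can show. The design can deliver between-program agreement and breath-hold repeatability. It cannot establish system accuracy.

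The size cannot be fixed from the documents. The 0.7 to 2.2 ratio rests on assumed SDs, equal and independent program errors, and shared error that acts equally on both programs. The cancellation does not depend on the SD values chosen, but it does depend on the last condition.

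This is a change that should be made because it governs what Arm 1 may conclude. It does not put the study's main accuracy evaluation in doubt.

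**What to change.** 1. **Wording.** In the Abstract, and in the two section 4a phrases about validating the tracking and evaluating software accuracy, replace the accuracy claim with agreement between two registration methods and breath-hold repeatability. Keep the workflow and reference-range aims. Reserve the word accuracy for the CBCT comparison in Arms 2 and 3.
2. **Analysis.** In section 7a, report the built-in-minus-Velocity difference for each axis, with limits of agreement from a model with a volunteer random effect. The limits should combine between- and within-volunteer variance, because each volunteer gives several scans.
3. **Conduct.** Perform the Velocity registration without sight of the built-in result, and say so in section 4a.

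Items 2 and 3 make the agreement estimate sound; they do not detect shared error. Only an independent reference could do that, and none is needed once the claim is narrowed.

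The cost is text changes and a small analysis of data already planned, with no added imaging or participants. The downside is that Arm 1 can no longer be cited as an accuracy validation.
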